TITLE: Randomized Clinical Trial Comparing Analgesia and Plasma Pharmacokinetics of Lidocaine administered by Erector Spinae Plane Blocks vs. Intravenous Routes Following Open Heart Surgery: An Equivalence Study

NCT Number: NCT04995497

[name]

Document Date: April 13, 2022

Protocol Outline

[figure not shown]
Protocol Title: Randomized Clinical Trial Comparing Analgesia and Plasma Pharmacokinetics of Lidocaine Administered by Erector Spinae Plane Blocks vs. Intravenous Routes Following Open Heart Surgery: An Equivalence Study

Protocol Version: 5

Protocol Date: April 13, 2022

Principal Investigator: [name]

Research Team: [name] [name]

I. Abstract

Recently interfascial plane blocks have been developed for analgesia including erector spinae plane (ESP) block. The ESP block has been hypothesized to provide truncal analgesia by spread of local anesthetic into the paravertebral space. However, recent studies have shown that the spread of local anesthetic by this block procedure into the paravertebral space is unreliable. It has been established that interfascial plane blocks can result in systemic levels of local anesthetic that can achieve therapeutic concentrations similar to those observed by intravenous infusions of local anesthetic and could likely be the mechanism of action of the ESP block. Free and total plasma lidocaine levels will be measured until steady state levels are achieved with ESP blocks. Additionally, the safety of the ESP block using doses of local anesthetic has not been rigorously evaluated. This study will evaluate both the analgesic efficacy and safety of ESP blocks in post-cardiac surgery

patients in comparison to intravenously administered lidocaine.

II. Background and Significance/Preliminary Studies

Postoperative pain is a significant issue following open heart surgery and poorly controlled pain can result in significant cardio-respiratory morbidity. A significant number of patients suffer from pain issues both at rest (49%) and on movement (62%) following open heart surgery via sternotomy (1,2) and adequate pain management requires closer re-assessment and treatment. The intensity of pain is noted to be higher in the first 48 hours post-surgery (3,4,5,6,7,8) and hence modalities to control pain may make the greatest difference in the first two days after surgery.

Enhanced recovery pathways utilizing multimodal analgesia have shown significant analgesic and opioid sparing benefit while minimizing ICU and length of hospital stays (9,10). Some such multimodal analgesic regimens have also incorporated regional anesthesia, but the optimal analgesic regimen is still elusive. Central neuraxial blocks such as epidural, intrathecal and paravertebral blocks have been utilized for cardiac surgery associated pain but given not widely adapted to practice due to concerns of altered coagulation status and the possibility of neuraxial hematoma. Additionally, there is a lack of clear guidelines to provide deeper regional nerve blocks in this patient population. A variety of interfascial plane blocks have been developed, among which the erector spinae plain (ESP) block has gained popularity recently. Given the non-neuraxial and superficial location of the structures of interest, more healthcare providers are offering ESP to provide analgesia following open heart surgery. Early evidence available from a clinical trial comparing ESP to no block and non-standardized multimodal anesthesia has shown variable pain reduction but consistent opioid sparing effects (11,12). The ESP block has been hypothesized to provide truncal analgesia by spread of local anesthetic (LA) into the paravertebral space (PVS). However, recent anatomical studies have contested this idea, showing unreliable spread of LA to the PVS. It is also well known that bilateral paravertebral blocks can result in higher than acceptable systemic levels of LA both in cardiac (13,14) and non-cardiac surgical patients and this may be true following bilateral ESP as well. Hence, the pharmacokinetic profile of administered local anesthetics is necessary given the lack of information about the local anesthetic systemic levels following bilateral ESP.

It is well known that interfascial plane blocks can result in systemic levels of LAs that achieve therapeutic concentrations (15) similar to that observed by intravenous infusions of LA (16,17). This is very likely the case for the ESP block, especially since the clinical and anatomical studies have conflicting findings regarding the loco-regional effects. Although intravenous lidocaine has shown some promise to prevent post-operative cognitive dysfunction (18,19), its effect on postoperative pain is not well studies. One study utilizing low dose lidocaine failed to show improvement in pain scores or opioid consumption, but the study did not utilize standardized multimodal analgesia

regimen (20). It is currently unknown whether the analgesic benefits of interfascial plane blocks are due to the multimodal analgesic regimen, the loco-regional benefits of the blocks, the systemic levels of local anesthetics following the block performance or a combination of all. We hypothesize that the mechanism by which the ESP block produces analgesia in the background of multimodal analgesia is probably related to the systemic absorption of local anesthetics. In addition, the safety of the ESP block using high doses of LA in cardiac surgery patients has not been rigorously assessed. We propose a pragmatic study to address both unknowns, the mechanism and safety of ESP following cardiac surgery.

III. Study Aims

- 1. The hypothesis of this study is that the analgesic effects of ESP can be attributed to its systemic distribution rather than its locoregional effects. A finding that lidocaine administered by ESP block achieves plasma concentrations in the analgesic range (2-5 ug/ml) at steady state will support our hypothesis whereas inability to reach analgesic levels will suggest that systemic distribution of local anesthetic is not a significant contributing factor of analgesia.
- 2. Despite the use of clinically acceptable doses, plasma concentrations of local anesthetic have been known to reach toxic levels following bilateral paravertebral blocks. This may also be true of ESP blocks. This study will address this concern and help establish a safety profile for ESP blocks in the cardiac patient population.

IV. Administrative Organization

University of Iowa Hospitals and Clinics—CVICU and Laboratories

V. Study Design

- i. Experimental design of the study (e.g., single-blind, double-blind): Randomized
- ii. Study population general description: Adults undergoing elective cardiac surgery for coronary artery bypass graft (CABG) or valve surgery via sternotomy
- iii. Sample size determination and power analyses: 70 adult patients as determined using an online calculator available at: https://www.sealedenvelope.com/power/continuous-equivalence/
- iv. Study outcomes/endpoints:
 - 1. Arterial blood samples will be drawn and assessed for lidocaine concentrations
 - 2. Pain scores will be collected from EPIC electronic medical record or directly from the subjects.
 - 3. Opioid doses will be assessed and reported in morphine equivalents

VI. Study Procedures

- a. Subject selection procedures
 - i. Inclusion: Any patient >18 years and <81 years undergoing elective cardiac surgery for CABG or valve surgery via sternotomy and surgical procedure is not greater than 12 hours

Exclusion: Allergy to study medications; major livor or kidney dysfunction; BMI <20 or >50; revision surgery; Off-pump coronary artery bypass surgery; surgery via thoracotomy; narcotic dependent (opioid intake morphine equivalent > 10 mg/day for more than 3 months); other sources of chronic pain such as fibromyalgia; patients with associated significant central nervous system, liver, renal or respiratory disease; coexisting hematological disorder or deranged coagulation parameters; lack of informed consent; preoperative neurological deficits; and emergency surgery (E1, E2 and E3 classifications only).

ii. Recruitment procedures

- **1. Where will recruitment occur?** Pre-surgical clinic or Day of Surgery Admissions (DOSA)
- **2.** Where and when will consent be obtained? DOSA prior to surgery or in pre-surgical clinic
- 3. Who will obtain consent? Anesthesia team
- 4. What is the advertising plan, if applicable? N/A
- 5. What recruitment materials will be provided to the potential participant (brochures/information sheets/video presentation)? None.

iii. Screening procedures

- 1. What procedures are required for screening? Prior to the surgical procedure, the anesthesia team will review eligibility criteria: Allergic to study medication; diagnosed with major liver or kidney dysfunction; any bleeding disorders; in females verify non-pregnant state.
- 2. What is the screening schedule (number of visits, length of visits)? This will occur only on the day of surgery and will last approximately 30 minutes.
- 3. Which screening tests/procedures are part of standard care and which are for research purposes only? All screening procedures listed above are part of standard of care.
- 4. What happens with screen failures (including any data gathered during screening)? A screening

log will be maintained and will be destroyed at upon study completion.

b. Randomization procedures (if applicable)

Participants will be randomized to IV or ESP groups using a computer-generated block randomization sequence and the allocation concealment will be ensured using a sealed envelope technique. The randomization sequence will be available with the PI and the research team.

c. Study Intervention

- iv. For Drug/device studies:
 - 1. Active study agents: Lidocaine
 - 2. Placebo study agents: None
 - **3. Blinding/labeling/preparation of agents:** Drug will be provided through the UIHC Investigational Drug Service
 - **4. Storage:** Room temperature. Protect from light.
 - **5. Administration:** Per study, either through ESP catheter or intravenously.
- 6. Toxicities and guidelines for adjustments: Acute emergencies from local anesthetics are generally related to high plasma levels encountered during therapeutic use of local anesthetics or to unintended subarachnoid injection of local anesthetic solution.

Management of Local Anesthetic Emergencies The first consideration is prevention best accomplished by careful and constant monitoring of cardiovascular and respiratory vital signs and the patient's state of consciousness after each local anesthetic injection. At the first sign of change, oxygen should be administered.

The first step in the management of convulsions, as well as underventilation or apnea due to unintended subarachnoid injection of drug solution, consists of immediate attention to the maintenance of a patent airway and assisted or controlled ventilation with oxygen and a delivery system capable of permitting immediate positive airway pressure by mask. Immediately after the institution of these ventilatory measures, the adequacy of the circulation should be evaluated, keeping in mind that drugs used to treat convulsions sometimes depress the circulation when administered intravenously. Should convulsions persist despite adequate respiratory support, and if the status of the circulation permits, small increments of an ultra-short acting barbiturate (such as thiopental or thiamylal) or a benzodiazepine (such as diazepam) may be administered intravenously. The clinician should be familiar, prior to the use of local anesthetics, with these anticonvulsant drugs. Supportive treatment of

circulatory depression may require administration of intravenous fluids and, when appropriate, a vasopressor as directed by the clinical situation (e.g., ephedrine).

If not treated immediately, both convulsions and cardiovascular depression can result in hypoxia, acidosis, bradycardia, arrhythmias and cardiac arrest. Underventilation or apnea due to unintentional subarachnoid injection of local anesthetic solution may produce these same signs and also lead to cardiac arrest if ventilatory support is not instituted. If cardiac arrest should occur, standard cardiopulmonary resuscitative measures should be instituted.

Endotracheal intubation, employing drugs and techniques familiar to the clinician, may be indicated, after initial administration of oxygen by mask, if difficulty is encountered in the maintenance of a patent airway or if prolonged ventilatory support (assisted or controlled) is indicated.

d. Study Assessments and Activities

- i. Describe all study procedures, assessments, and subject activities Procedures Affecting Both Groups
 - A. Pre-Operative Phase (Standard of Care)
 - Pre-operative fasting and carbohydrate treatment. Patients are kept NPO for 8 hours before surgery except for an oral carbohydrate beverage given 2 4 hours before procedure.
 - Pre-operative multimodal analgesic is initiated. Gabapentin and acetaminophen will be given pre-operatively and continued postoperatively at regular intervals.
 - Anxiolytic medications. Minimal anxiolytic medications given before surgery including midazolam given by anesthesia provider.
 - B. Intra-Operative Phase (Standard of Care At discretion of Anesthesia Provider)
 - Intraoperative opioid administration. Fentanyl IV given as needed for pain but typically < 1 mg for procedure.
 - Hydromorphone 0.5 1 mg given near completion of procedure
 - Intraoperative multimodal analgesia. If time since preoperative acetaminophen dose significantly exceeds 6 hours, acetaminophen 1000 mg IV, or via NG route is considered
 - Postoperative sedation initiated. Near the end of the procedure, dexmedetomidine or propofol infusion is begun for postoperative sedation in ICU while intubated

• All patients will receive dual post-operative nausea and vomiting (PONV) prophylaxis in the form of ondansetron and dexamethasone at appropriate time periods.

If the surgical procedure takes longer than 12 hours, the subject will be withdrawn from the study.

C. Block Performance/Procedure

• Upon arrival to the CV-ICU, patients will be assessed for eligibility to extubate based on hemodynamic and pulmonary stability on a case-by-case basis with the aim to extubate as early as possible. When appropriate, extubation will proceed following the CV-ICU Fast Track Extubation protocol that is already in place. Extubation is not required prior to the administration of study drug via IV or ESP catheters route. Participation in the study can proceed as long as after assessment by clinicians, the subject is extubated or ready to be extubated.

[figure not shown]
D. Group ESP (Study Procedures)

- Bilateral ultrasound guided erector spinae plane (ESP) catheters will be inserted either pre- or post-operatively.
- After confirming that there are no contra-indications, the subject will receive lidocaine via ESP catheter.
- Patients will receive lidocaine at a dose of 2 mg/kg ideal body weight (IBW) as bolus divided equally between the two ESP catheters.
- Subjects will then lie in a supine position.
- Lidocaine infusion via ESP catheters either through 2 dedicated pumps or via a single pump and a y-connector at a rate of 2 mg/kg/hour for approximately 48 hours.
- Blood samples will be drawn at 5, 30, 60, 120 minutes, 6 and 24 hours and assessed for lidocaine concentration.
- Pain scores (resting and with movement/cough) will be collected from bedside record and EPIC medical record. Standard assessment protocol already in place has this charted every 2 4 hours by ICU nursing staff.
- All patients will receive continued oral multimodal analgesia
- When not eligible to receive oral medications (e.g. NPO), pain analgesia will be provided through an IV route. This can include an IV PCA pump using hydromorphone 0.2 mg with a lockout of 10 minutes and a maximum dose of 6 mg in 4 hours continued postoperatively.
- If oral medications are insufficient to provide pain relief, and the subjects are not receiving medications via PCA, pain medications

will be provided IV. • Opioid doses (both oral and IV) will be assessed and reported in morphine equivalents.

E. Group IV (Study Procedures)

- Patients will receive lidocaine at a dose of 2 mg/kg ideal body weight (IBW) through IV route.
- Subjects will then lie in a supine position.
- Lidocaine infusion via IV route at a rate of 2 mg/kg/hour for approximately 48 hours.
- Blood samples will be drawn at 5, 30, 60, 120 minutes, 6 and 24 hours and assessed for lidocaine concentration.
 - Pain scores (resting and with movement/cough) will be collected from bedside record and EPIC medical record. Standard assessment protocol already in place has this charted every 2 4 hours by ICU nursing staff
 - All patients will receive continued oral multimodal analgesia
- When not eligible to receive oral medications (e.g. NPO), pain analgesia will be provided through an IV route. This can include an IV PCA pump using hydromorphone 0.2 mg with a lockout of 10 minutes and a maximum dose of 6 mg in 4 hours continued postoperatively.
- If oral medications are insufficient to provide pain relief, and the subjects are not receiving medications via PCA, pain medications will be provided IV.
- Opioid doses (both oral and IV) will be assessed and reported in morphine equivalents.
- ii. Provide a schedule of all study assessments and subject activities, including a tabular representation or timeline as applicable

VII. Safety Monitoring Plan

i. Definition of adverse events, serious adverse events:

An adverse event (also referred to as an adverse experience) can be any unfavorable and unintended sign (e.g., an abnormal laboratory finding), symptom, or disease temporarily associated with the use of a drug, without any judgment about causality or relationship to the drug.

An adverse event or suspected adverse reaction is considered "serious" if, in the view of either the investigator or sponsor, it results in any of the following outcomes: Death, a life-threatening adverse event, inpatient hospitalization or prolongation of existing hospitalization, a persistent or significant incapacity or substantial disruption of the ability to conduct normal life functions, or a congenital anomaly/birth defect.

Any adverse experience that places the subject, in the view of the investigator, at immediate risk of death from the reaction as it occurred, or it is suspected that the use or continued use of the product would result in the patient's death.

ii. What procedures will be used to monitor subject safety?

Careful and constant monitoring of cardiovascular and respiratory (adequacy of ventilation) vital signs and the patient's state of consciousness should be accomplished. It should be kept in mind at such times that restlessness, anxiety, tinnitus, dizziness, blurred vision, tremors, depression or drowsiness may be early warning signs of central nervous system toxicity.

For the purpose of being prepared to deal with the side effects of lidocaine (Bradyarrhythmia, hypotension, infusion site reactions), the blocks will only be performed in the Cardiac ICU, where pharmacological and non-pharmacological measures are available to treat these side effects. The foundation of local anesthetic toxicity is outlined in seizure management with pharmacological seizure management, advanced cardiac life support (ACLS) to support the heart and use of 20% lipid emulsion to reverse local anesthetic toxicity. Oxygen can be provided for patients needing improved oxygenation and all the emergency medications, pharmacists and intensivists are readily available in the ICU.

- iii. Who (list names) will identify, document, and report adverse events? Nursing staff in the CVICU should report adverse events to [name] or [name] within 12 hours of the event. After the subject is stabilized this information will be reported to a member of Anesthesia Innovative Research Core who will report the event to the IRB.
- iv. What is the frequency for review of summarized safety information and who will perform the review (e.g., safety monitoring board)?

No committee is currently in place for this pilot study.

v. What are the stopping rules with regard to efficacy and safety?

If an adverse/serious adverse event occurs, the study will be paused until careful evaluations is performed.

VIII. Analysis Plan

Study variables will be collected and tabulated. The continuous and discrete variables will be presented as mean and standard deviation after calculation and the categorical variables will be presented as frequencies. Normality of distribution will be assessed using Q-Q plots followed by Shapiro-Wilk test. Normally distributed data will be assessed using independent sample t-test and non-normally distributed data will be assessed using Mann-Whitney U-test. Categorical variables will be tested using chi-square tests or Fisher's exact test. Tests for equivalence will be applied for the primary outcome measures

failing which, tests of superiority will be applied. P values <0.05 will be considered statistically significant.

IX. Literature Cited

- 2. LahtinenP, Kokki H, Hynynen M. Pain after cardiacsurgery: A prospective cohort study of 1-year incidence and intensity. Anesthesiology. 2006;105 (4):794–800. doi:10.1097/00000542-200610000-00026
- 5. Reimer-Kent J. From theory to practice: preventing pain after cardiac surgery. Am J Crit Care. 2003;12(2):136–143.

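### Aim 1 reads an in-range ESP plasma level as support for a systemic rather than locoregional effect, but that level fits both explanations, and the rule uses neither the IV arm nor any analgesic outcome

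*Combined protocol and SAP*

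**What the plan says.** Section III, item 1 gives the hypothesis that "the analgesic effects of ESP can be attributed to its systemic distribution rather than its locoregional effects". It then gives a two-way reading rule. The favourable branch is: "A finding that lidocaine administered by ESP block achieves plasma concentrations in the analgesic range (2-5 ug/ml) at steady state will support our hypothesis". The unfavourable branch follows: "whereas inability to reach analgesic levels will suggest that systemic distribution of local anesthetic is not a significant contributing factor of analgesia". Both branches refer to the plasma level reached with ESP. Neither mentions the IV arm, pain scores or opioid use.

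Elsewhere the argument is comparative. The Abstract (Section I) rests the systemic explanation on "systemic levels of local anesthetic that can achieve therapeutic concentrations similar to those observed by intravenous infusions of local anesthetic", and Section II on levels "similar to that observed by intravenous infusions of LA". Section II also lists the explanations still open: the multimodal regimen, the local effect of the block, and "the systemic levels of local anesthetics following the block performance or a combination of all". It ends by offering the study as a way to address both mechanism and safety.

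The design matches that argument. The title calls it an equivalence study of analgesia and pharmacokinetics by two routes. Patients are randomised to ESP or IV (Section VI.b). Both groups have the same nominal infusion rate of 2 mg/kg/hour, the same sampling times to 24 hours, and the same pain and opioid recording (Section VI.d, Groups ESP and IV). Section VIII plans equivalence tests, then superiority tests, on primary outcome measures that it does not name.

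**The concern.** A result supports one explanation over another only if it is more likely under the first. An in-range plasma level is expected whenever enough lidocaine is absorbed, wherever the pain relief arises. The favourable branch therefore cannot carry the exclusive claim in the hypothesis.

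The two branches also answer different questions. The hypothesis is exclusive (systemic and not local), while the unfavourable branch speaks only of systemic distribution as a contributing factor. The natural counterpart of that branch is that systemic lidocaine may contribute, which is weaker than the hypothesis.

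Mechanism is one of the two unknowns the study exists to address. If the rule is followed as written, an in-range ESP level would be reported as support for a systemic mechanism even if patients with ESP had clearly better analgesia than patients with IV lidocaine at the same plasma level. The between-arm data that could show this will be collected, but the plan does not say how they bear on Aim 1.

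**Working it through.** **1. Does an in-range level discriminate?** With complete absorption, the steady-state level is infusion rate divided by clearance by either route. The rate is 2 mg/kg/h in both arms (Section VI.d). The documents give no clearance, so I solve for it: 2/5 = 0.4 and 2/2 = 1.0. Any clearance from 0.4 to 1.0 L/h/kg gives 2-5 ug/ml, whether or not the block also acts locally.

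In likelihood terms, assume an in-range level has probability 0.9 under a systemic mechanism and a prior of 50%:

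| P(in range) under a locoregional mechanism (assumed) | Likelihood ratio | Posterior for systemic |
|---|---|---|
| 0.9 | 0.9/0.9 = 1.0 | 50% |
| 0.5 | 0.9/0.5 = 1.8 | 64% |
| 0.1 | 0.9/0.1 = 9 | 90% |

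The last row needs in-range levels to be rare when the block acts locally. That sits badly with Section II, which treats therapeutic levels after interfascial plane blocks as well known and reports high levels after bilateral paravertebral blocks.

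**2. Would the randomised comparison respond where the rule does not?** Inputs: 70 patients (Section V.iii), with 35 per arm and no losses assumed. Take a true ESP advantage of 0.7 SD on an analgesic outcome, a value chosen only for illustration. The plasma criterion does not change. A two-sided t-test at 0.05 has power 0.823. An equivalence test (two one-sided tests at 0.05) declares equivalence with probability 0.053 at a margin of 0.707 SD and 0.105 at 0.794 SD. Because 0.7 SD lies inside both margins, these are not false-positive rates.

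**3. How precise is the exposure comparison?** On the log scale, SD = sqrt(ln(1 + CV²)), and the 90% CI for the ESP/IV ratio multiplies and divides by exp(t × SD × sqrt(2/35)), with t = 1.668 on 68 df. An assumed CV of 30% gives SD 0.294 and a factor of 1.124. An assumed CV of 50% gives SD 0.472 and a factor of 1.207. The ratio is worth reporting with its interval.

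**4. What margin can 70 patients support on an analgesic outcome?** The plan's 70 cannot be reproduced, because its margin, SD, power and outcome are not stated. Solving backwards with a true difference of 0, margin/SD = (z(1-α) + z(1-β/2)) × sqrt(2/35), where sqrt(2/35) = 0.239:

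| One-sided α | Power | Normal formula | With the t distribution |
|---|---|---|---|
| 0.05 | 80% | (1.645 + 1.282) × 0.239 = 0.70 | 0.707 |
| 0.05 | 90% | (1.645 + 1.645) × 0.239 = 0.79 | 0.794 |
| 0.025 | 80% | (1.960 + 1.282) × 0.239 = 0.77 | 0.786 |
| 0.025 | 90% | (1.960 + 1.645) × 0.239 = 0.86 | 0.874 |

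A margin this wide limits what equivalence can show. At one-sided 0.05, a true local benefit of 0.3 SD is still declared equivalent with probability 0.51 (margin 0.707) or 0.65 (margin 0.794).

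**The case against.** The strongest reply is that the comparison is already there. The title, the close of Section II and the equivalence sentence in Section VIII together offer an ESP-versus-IV study as the route to mechanism. This stands in part. A reader might infer that the protocol has no comparative approach to mechanism, and the documents do not support that. What is missing is a rule for reading the comparison within Aim 1.

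A second reply is that the wording is modest: the finding is said to support the hypothesis, not prove it, and Section II calls the mechanism only probable. But support still needs a result that favours one explanation over the other, and step 1 shows that this one need not.

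Two stronger readings are tempting and should not be adopted:

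- **Equal analgesia at a lower ESP level shows a local effect.** Suppose clearance is 0.45 L/h/kg and absorption 50% (both assumed). IV would be 2/0.45 = 4.4 ug/ml and ESP half of that, 2.2. Both lie inside the protocol's own analgesic range, so equal pain also fits a flat response within that range, or the multimodal regimen both arms share. It does not discriminate.
- **The unfavourable branch is wrong.** A low ESP level is informative. If both arms were below 2 ug/ml with equal analgesia (for example 2/1.1 = 1.8 ug/ml with an assumed clearance of 1.1 L/h/kg and full absorption), the shared regimen is an obvious explanation, and doubting a systemic contribution is defensible. The fair point is only that this branch is better read beside the IV arm.

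**Conclusion.** The concern holds. The favourable branch of Aim 1 is wrong as an inference, not merely short of detail: an in-range ESP level is compatible with a systemic mechanism but not specific to it, and it does not exclude a locoregional contribution. This conclusion rests on the protocol's wording and on the fact that locally acting lidocaine is absorbed. It needs none of the assumed clearances, absorption fractions or CVs, which serve only as illustration.

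The consequence is a possibly unsound mechanism conclusion, correctable in the text before results are seen. It should be fixed, but it does not undermine the randomised comparison. A reader might also infer that 70 patients are too few. The documents do not support that either, since they do not say which outcome 70 was sized for. One can say only that an analgesic equivalence claim would carry a margin of about 0.71-0.79 SD (one-sided 0.05) or 0.79-0.87 SD (one-sided 0.025) at 80-90% power, with 35 per arm and no losses assumed.

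**What to change.** Reword Aim 1 and Section VIII as follows.

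1. State that an in-range ESP level shows only that a systemic contribution is possible and does not exclude a locoregional one.
2. Base the mechanism reading on the randomised comparison already planned. Report the ESP/IV concentration ratio with its confidence interval next to the between-arm difference in one named analgesic outcome. Show both pain and opioid use, because opioid use can even out pain scores.
3. Treat better analgesia with ESP at similar or lower plasma levels as pointing to a locoregional contribution. Read it with caution, because no blinding of patients or pain assessors is described: Section V.i answers "Experimental design of the study (e.g., single-blind, double-blind): Randomized" and Section VI.c lists "Placebo study agents: None". Treat equal analgesia at lower ESP levels as not discriminating.
4. Interpret an ESP level below 2 ug/ml alongside the IV arm's level and analgesia.
5. Because there is no arm without lidocaine, report equivalence as no benefit of ESP beyond IV lidocaine larger than the margin, and not as proof of a systemic mechanism.

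The changes need no new arm, sample or visit. The costs are a narrower mechanism claim and the need to name an analgesic outcome and justify its margin, for which the documents give no basis. The achievable margin should be reported rather than 70 being asserted as adequate. A formal rule requiring both comparable exposure and equivalent analgesia is a possible further step, but it is a debatable design choice and this point does not depend on it.

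### Aim 1 turns on whether the ESP arm reaches 2-5 ug/ml, but the Analysis Plan has only between-arm tests and a mean and SD, so the verdict has no allowance for sampling error or for patients below 2 ug/ml

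*Combined protocol and SAP*

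**What the plan says.** Section III, item 1 gives the criterion in two branches. The supporting branch reads: "A finding that lidocaine administered by ESP block achieves plasma concentrations in the analgesic range (2-5 ug/ml) at steady state will support our hypothesis". The contrary branch reads: "inability to reach analgesic levels will suggest that systemic distribution of local anesthetic is not a significant contributing factor of analgesia". Neither says whether reaching the range is judged on a mean, a median or each patient. Neither names the sample that represents steady state.

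Section VI.d schedules blood at 5, 30, 60 and 120 minutes and at 6 and 24 hours in both groups, and labels none of these as steady state. The Abstract says that free and total lidocaine will both be measured. The aim does not say to which of them 2-5 ug/ml applies.

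Section VIII is the whole analysis plan. On summaries it says: "The continuous and discrete variables will be presented as mean and standard deviation after calculation"; categorical variables get frequencies. The tests are the independent-sample t-test or Mann-Whitney, chi-square or Fisher's exact, and equivalence followed by superiority for the primary outcome measures, with "P values <0.05 will be considered statistically significant". No confidence interval is mentioned. Section V, item iii gives the size as "70 adult patients as determined using an online calculator" for continuous equivalence.

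**The concern.** The aim asks a one-sample question, and the plan answers a two-sample one. Whether ESP levels resemble IV levels says nothing about whether either lies above 2 ug/ml, so the comparison on which the trial was sized cannot settle the hypothesis that the protocol states.

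What remains is a descriptive ESP summary set against the threshold. That gives two possible readings and no third for data too imprecise to tell. A group summary inside the range can also coexist with a sizeable minority of ESP patients below 2 ug/ml, and the plan does not require that minority to be counted. Because the statistic, time point and analyte are open, they could be chosen after the levels are known. At stake is the trial's mechanistic conclusion, not the soundness of the data.

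**Working it through.** **1. The plan's own figure.** The only stated number is 70 patients, from a two-arm equivalence calculator. Margin, SD, power, sidedness and allocation ratio are not given; the ratio is absent from "Participants will be randomized to IV or ESP groups using a computer-generated block randomization sequence". The figure can therefore only be back-solved, assuming 1:1 (35 per arm).

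n per arm = 2 × (z(1−α) + z(1−β/2))² × (SD/margin)², so margin/SD = (z(1−α) + z(1−β/2)) × √(2/35).

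| One-sided α | Power | Margin/SD |
|---|---|---|
| 0.05 | 80% | (1.645 + 1.282) × 0.239 = 0.70 |
| 0.05 | 90% | (1.645 + 1.645) × 0.239 = 0.79 |
| 0.025 | 80% | (1.960 + 1.282) × 0.239 = 0.77 |
| 0.025 | 90% | (1.960 + 1.645) × 0.239 = 0.86 |

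So 70 is attainable but not verifiable. Nothing here shows it to be wrong, but it was not derived for Aim 1's threshold question.

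**2. Can the listed tests answer Aim 1?** An equivalence test on means depends on the ESP-minus-IV difference and its standard error. For a given spread, arms at 1.5 and 1.5 ug/ml pass exactly as readily as arms at 3.0 and 3.0. The first pair contradicts the hypothesis under Aim 1 and the second supports it. The t-test, Mann-Whitney, chi-square and Fisher tests also compare groups. The only one-sample procedure in section VIII is the Shapiro-Wilk check of normality.

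**3. Sampling error left out of the verdict.** Assumptions, since the documents give no variance: 35 ESP patients with no loss, log-normal levels, between-patient log-SD s of 0.3, 0.4 or 0.5. The 95% interval for the geometric mean is the estimate divided and multiplied by exp(t × s/√35), with t on 34 df = 2.032.

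| s | s/√35 | Factor | Observed geometric means whose interval includes 2 ug/ml |
|---|---|---|---|
| 0.3 | 0.0507 | 1.109 | 2/1.109 to 2 × 1.109 = 1.80 to 2.22 |
| 0.4 | 0.0676 | 1.147 | 1.74 to 2.29 |
| 0.5 | 0.0845 | 1.187 | 1.68 to 2.37 |

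In those zones the data would not separate the two branches, yet the aim provides only two.

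**4. Patients below 2 ug/ml behind an in-range group value.** Share below 2 = Φ(ln(2/GM)/s). At GM = 2.5, ln(0.8) = −0.223:

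- s = 0.3: Φ(−0.744) = 23%
- s = 0.4: Φ(−0.558) = 29%
- s = 0.5: Φ(−0.446) = 33%

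**5. Precision of the counts.** If 28 of 35 ESP patients reached 2 ug/ml (80%), the exact 95% interval would be 63-92%. With 24 of 35 (69%) it would be 51-83%.

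**The case against.** The strongest reply is that the protocol's language is modest. It speaks of results that support or suggest, and section VII calls this a pilot study. It nowhere says that the group mean decides the matter. Section VIII allows frequencies, so a per-patient share could be tabulated, and a reader could build an interval from mean, SD and n. All of this is true. The gap is therefore one of pre-specification: the uncertainty is recoverable, but no statistic, cut-off variable or interval is fixed in advance.

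Three stronger readings are tempting and should not be drawn.

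- *That the rule is close to a coin toss near 2 ug/ml.* Under the model above, a true geometric mean of 1.9 gives a sample geometric mean above 2 in 16-27% of trials, but a sample arithmetic mean above 2 in 44-78% (simulated). At 2.1 the chance of falling below 2 is 17-28% on the geometric mean and about 3-4% on the arithmetic mean. The rates depend on which mean is used, and nothing in the documents places ESP levels near the cut-off. They are not a property of the plan.
- *That some patients never reach 2 ug/ml, or that a systemic explanation cannot hold for them.* The calculation concerns one time point, and the protocol does not present 2 ug/ml as an absolute limit for each individual.
- *That a level above 5 ug/ml falls outside the rule.* It is outside the stated range but has plainly reached analgesic levels, so the gap is minor. Aim 2 speaks of toxic levels without giving a figure.

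An interval on a group mean also does not by itself cure the hidden-minority problem. At a true geometric mean of 2.5, a rule requiring the lower limit to be at least 2 is met in 73-99% of trials, with the same 23-33% of patients below 2. The counts must therefore be part of the stated conclusion.

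**Conclusion.** The point holds as a gap in pre-specification. Aim 1's criterion is a one-arm comparison with a fixed threshold, and section VIII contains no analysis that addresses it. This follows from the text and needs no assumption about variance.

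The size does rest on assumptions: 35 ESP patients from an assumed 1:1 split, log-normal levels and log-SD 0.3-0.5. On these, uncertainty of about 11-19% each way goes unstated, and about a quarter to a third of ESP patients could be below 2 ug/ml while the group value is 2.5. If true levels lie well away from 2 ug/ml, the verdict would seldom change. The documents give no basis for saying whether they do. It should be corrected before the levels are analysed. It does not invalidate the data or the sample size.

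**What to change.** Add to section VIII, for Aim 1:

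1. Name the steady-state sample from those already scheduled (for example the 24-hour sample), and say whether 2-5 ug/ml refers to free or total lidocaine.
2. Report the ESP geometric mean at that sample with a 95% confidence interval. The verdict is *reached* if the lower limit is at least 2 ug/ml, *not reached* if the upper limit is below 2 ug/ml, and *inconclusive* otherwise.
3. State the conclusion together with the numbers of ESP patients below 2, within 2-5 and above 5 ug/ml, with exact 95% intervals, so that a group verdict is not read as applying to every patient.
4. Label any comparison of pain or opioid use by lidocaine level as descriptive. Level is observed after randomisation, so such a contrast is not protected by it.

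The cost is SAP wording and one table, using samples already planned. No dose, procedure or sample size changes. The price for the investigators is that the verdict on Aim 1 may be *inconclusive*.
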